Screening procedures will be conducted after informed consent is obtained (refer to Section 10.1.3) and within 7 days before anticipated hospital discharge and enrollment/randomization (Day 1). If informed consent and screening activities are conducted on the same day as enrollment/randomization (Day 1), assessments should not be duplicated. All screening evaluations must be completed and reviewed to confirm that potential participants meet all eligibility criteria. The investigator will maintain a screening log to record details of all participants screened and to confirm eligibility or record reasons for screening failure, as applicable.

On Day 1, after all eligibility criteria are verified, eligible participants will be enrolled and randomized. Randomization should take place at the time of hospital discharge. Refer to Section 6.2 for randomization.

Procedures conducted as part of the participant's routine clinical management (e.g., procedures while hospitalized) and obtained before the ICF is signed, may be utilized for screening or baseline purposes provided the procedures met the protocol-specified criteria and were performed within the time frame defined in the SoA (Table 2).

Adherence to the study design requirements, including those specified in the SoA is essential and required for study conduct.

Immediate safety concerns should be discussed with the sponsor immediately upon occurrence or awareness to determine if the participant should continue or discontinue study intervention.

Study procedures and their timing are summarized in the SoA (Table 2). Protocol waivers or exemptions are not allowed.

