8.3.1. Medical History and Full Physical Examination

A full medical history, including medications and vaccinations received, will be recorded at screening to assess enrollment eligibility and to provide a baseline.

All conditions that exist before and during screening will be recorded in the medical history. The infant's HIV status, including history of HIV exposure, will also be recorded. Physical examination at screening will include, at a minimum, assessment of all planned anthropometric measurements, including weight to assess WAZ, length to measure WLZ score, MUAC, head circumference, and skinfold thickness. Details regarding standardized anthropometric measurements will be provided in the Study Manual. Presence of bilateral pedal edema will also be assessed.

In addition, resting vital signs, including body temperature (refer to Section 8.3.3) and other assessments of eligibility criteria requiring a physical examination will be performed.

A complete physical examination will include, at a minimum, assessments of the head, eyes, ears, nose and throat, cardiovascular, respiratory, gastrointestinal, musculoskeletal, and neurological systems.

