8.4.1. Time Period and Frequency for Collecting AE and SAE Information

All AEs and SAEs will be collected from the time the informed consent is signed through the EoS (Day 90 visit or at the Discontinuation Visit, as applicable). All AEs and SAEs will be classified according to the *Medical Dictionary for Regulatory Activities* (MedDRA).

All SAEs will be recorded and reported to the sponsor or designee immediately within 24 hours, as indicated in Section 10.2.4. The investigator will submit any updated SAE data to the sponsor within 24 hours of it being available.

Investigators are not obligated to actively seek AE or SAE information after conclusion of the study participation. However, if the investigator learns of any SAE, including a death, at any time after a participant has been discharged from the study, and if the investigator considers the event to be reasonably related to the study intervention or study participation, the investigator must promptly notify the sponsor.

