10.2.1. Definition of AE

AE Definition

An AE is any untoward medical occurrence in a patient or clinical study participant, temporally associated with the use of study intervention, whether or not considered related to the study intervention.

NOTE: An AE can therefore be any unfavorable and unintended sign (including an abnormal laboratory finding), symptom, or disease (new or exacerbated) temporally associated with the use of study intervention.

Events Meeting the AE Definition

Any abnormal laboratory test results (hematology, clinical chemistry, or urinalysis) or other safety assessments (e.g., ECG, radiological scans, vital signs measurements), including those that worsen from baseline, considered clinically significant in the medical and scientific judgment of the investigator (i.e., not related to progression of underlying disease).

Exacerbation of a chronic or intermittent pre-existing condition including either an increase in frequency and/or intensity of the condition.

New conditions detected or diagnosed after study intervention administration even though it may have been present before the start of the study.

Signs, symptoms, or the clinical sequelae of a suspected drug-drug interaction.

Signs, symptoms, or the clinical sequelae of a suspected overdose of either study intervention or a concomitant medication. Overdose per se will not be reported as an AE/SAE unless it is

an intentional overdose taken with possible suicidal/self-harming intent. Such overdoses should be reported regardless of sequelae.

Events **NOT** Meeting the AE Definition

Any clinically significant abnormal laboratory findings or other abnormal safety assessments which are associated with the underlying disease, unless judged by the investigator to be more severe than expected for the participant's condition.

The disease/disorder being studied or expected progression, signs, or symptoms of the disease/disorder being studied, unless more severe than expected for the participant's condition.

Medical or surgical procedure (e.g., endoscopy, appendectomy): the condition that leads to the procedure is the AE.

Situations in which an untoward medical occurrence did not occur (social and/or convenience admission to a hospital).

Anticipated day-to-day fluctuations of pre-existing disease(s) or condition(s) present or detected at the start of the study that do not worsen.

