10.2.3. Recording and Following Up SAEs

SAE Recording

- Care will be taken not to introduce bias when detecting SAEs. Open-ended and non-leading verbal questioning of the participant is the preferred method to inquire about occurrences.
- When an SAE occurs, it is the responsibility of the investigator to review all documentation (eg, hospital progress notes, laboratory reports, and diagnostics reports) related to the event.
- The investigator will then record all relevant SAE information in the eCRF.
- After the initial SAE report, the investigator is required to proactively follow each participant at subsequent visits/contacts. All SAEs will be followed until resolution, stabilization, the event is otherwise explained, or the participant is lost to follow-up.
- It is **not** acceptable for the investigator to send photocopies of the participant's medical records to the sponsor in lieu of completion of the SAE eCRF page.
- There may be instances when copies of medical records for certain cases are requested by the Medical Monitor, the IDMC or the sponsor. In this case, all participant identifiers, with the exception of the participant number, will be redacted on the copies of the medical records before submission.

- The investigator will attempt to establish a diagnosis of the event based on signs, symptoms, and/or other clinical information. Whenever possible, the diagnosis (not the individual signs/symptoms) will be documented as the SAE.
- SAEs will be assessed for intensity and causal relationship to the study intervention.

SAE Follow-up and Resolution

The investigator is obligated to perform or arrange for the conduct of supplemental measurements and/or evaluations as medically indicated to elucidate the nature and/or causality of the SAE as fully as possible. This may include additional laboratory tests or investigations, histopathological examinations, or consultation with other health care professionals.

If a participant dies during participation in the study or during a recognized follow-up period, the investigator will provide the sponsor with a copy of any post-mortem findings including histopathology, if available.

New or updated information will be recorded in the originally completed eCRF.

The investigator will submit any updated SAE data to the sponsor within 24 hours of receipt of the information.

The onset and resolution dates of the event and medical care taken in response to the event will be documented.

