11.6.1 Adverse Events

Safety assessments include SAEs and AEs from the time the ICF is signed through Day 90 (or at the date of last visit/study discontinuation).

An AE is considered treatment emergent if it started on or after the date of first dose of study intervention administration.

Confidential Page 37 of 50

An AE overview table containing the number and percentage (expressed in percent) of participants with AEs from Day 1 through Day 90 will be summarized by treatment group for the following:

- Any AE
- Any TEAE
- TEAEs related to study intervention
- TEAEs by maximum severity (Mild, Moderate and Severe)
- TEAEs leading to study intervention discontinuation
- TEAEs leading to study withdrawal
- Serious TEAEs
- Serious TEAEs with Outcome of Death

Additionally, the number and percentage of participants with AEs will be provided by SOC and PT and by treatment group for the following:

- Any TEAE
- TEAEs by maximum severity
- TEAEs related to study intervention
- Serious TEAEs
- Serious TEAEs related to study intervention

By-period summaries will be presented for TEAE and serious TEAEs by treatment group, where period is defined as in Section 10.1.

The overall AE summary table, AE table by SOC and PT and SAE table by SOC and PT will be presented by subgroups as specified in Section 8.2.

All AEs and SAEs will be classified according to the latest version of MedDRA.

SOC and PT will be sorted alphabetically by SOC and by decreasing frequency of preferred term in the all Bi-26 group (then alphabetically for ties). If a participant has more than one AE at a given level (eg, SOC and preferred term), the participant will only be counted once within that level. All summary tables will include the number of AEs. Missing severities and relationship will not be regarded as 'worst case'.

The following listings will be presented:

- All AEs through to Day 90
- SAEs through to Day 90

The AE listing by participant will display all reported AEs up to Day 90 and will include the verbatim term in addition to the SOC and preferred term. This listing will also include all relevant data associated with the event: eg, date of onset, date resolved, date of first dose, date of last dose, severity, whether AE is serious, outcome, relationship to study intervention, action taken with study intervention, and required therapy. When a date is presented, the study day

Confidential Page 38 of 50

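### The SAP defines treatment-emergent AEs by start date alone, so events that open between consent and first dose and worsen under the same record are missing from the by-arm severity, serious and death summaries

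*SAP*

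**What the plan says.** - **Treatment-emergence rule, SAP 11.6.1:** "An AE is considered treatment emergent if it started on or after the date of first dose of study intervention administration". Nothing is said about an event that starts earlier and worsens later.
- **What counts as an AE, Protocol 10.2.1:** the list includes "Exacerbation of a chronic or intermittent pre-existing condition including either an increase in frequency and/or intensity of the condition" and "New conditions detected or diagnosed after study intervention administration even though it may have been present before the start of the study".
- **When collection starts, Protocol 8.4.1:** "All AEs and SAEs will be collected from the time the informed consent is signed through the EoS". Protocol Section 8 allows screening up to 7 days before discharge and Day 1, or on Day 1 itself. Protocol 8.3 adds that events between screening and Visit 1 may be taken from hospital records.
- **Medical history, Protocol 8.3.1:** "All conditions that exist before and during screening will be recorded in the medical history".
- **SAE follow-up, Protocol 10.2.3:** "New or updated information will be recorded in the originally completed eCRF", and "The onset and resolution dates of the event and medical care taken in response to the event will be documented". Neither document says which onset date applies when an open event worsens, or whether a new record is started.
- **Outputs, SAP 11.6.1 and 11.6.2:** apart from the any-AE row of the overview table, every by-arm AE row and table is limited to TEAEs. Deaths outside that set appear only in a participant listing.

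**The concern.** Safety through Day 90 is a stated objective, and the infants have only just come through an acute illness. One harm worth looking for is an event already present at discharge that deteriorates once a live organism is given. A rule that looks only at the start date can classify such an event as not treatment-emergent although the deterioration came after dosing. For these events the error runs one way: it removes severe, serious or fatal outcomes from the between-arm tables and cannot add any. The only death row in the AE tables could then show fewer deaths than occurred after dosing.

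**Working it through.** No figure in the plan is at stake, so the check is mainly a reading of the rules against each other.

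**Step 1. Can an AE record have a pre-dose start date?** Yes. Collection runs from consent, and consent may precede Day 1 by up to 7 days. Where screening takes place on Day 1 the window closes, because the SAP rule works on the date and counts any Day 1 event as treatment-emergent.

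**Step 2. How does the SAP rule classify each route?**

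| Route | Recorded start | TEAE? |
|---|---|---|
| (a) Medical-history condition that worsens after dosing, entered as an AE with its own onset | After dosing | Yes |
| (b) Pre-dose event that resolves, then recurs as a new event | After dosing | Yes |
| (c) Event opened between consent and first dose, still open, then worse, serious or fatal under the same record | Before dosing | No |
| (d) Condition first detected after dosing but recorded with its earlier onset | Before dosing | No |
| (e) Start on Day 1, start date wholly missing, or partial date in the month or year of first dose (SAP Appendix 2, Table 6) | Set to, or treated as, on or after first dose | Yes |

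Routes (c) and (d) are the gap. For SAEs, the instruction to update the original eCRF makes (c) a natural outcome. For non-serious AEs the documents give no instruction. Medical history and AE collection also overlap between consent and first dose, and no passage says which takes the event, so two sites could record the same course as (a) or as (c).

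**Step 3. Which outputs lose (c) and (d)?**

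| Output | Restricted to TEAEs? |
|---|---|
| Overview rows: maximum severity, related, discontinuation, withdrawal, serious, serious with fatal outcome | Yes |
| All SOC/PT tables | Yes |
| By-period tables | Yes |
| Any-AE overview row | No, but the table covers Day 1 to Day 90, so inclusion of an earlier start is unclear |
| AE, SAE and death listings | No |

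**Step 4. Scale.** Inputs from Protocol 9.4: 3% assumed mortality, 396 randomized, 198 per arm.

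- Expected deaths in total = 0.03 × 396 = 11.9.
- Expected deaths per arm = 0.03 × 198 = 5.9.
- Deaths missing from the row = 11.88 × s, where s is the share of deaths recorded against an event with a pre-dose start. The documents do not give s. The values below are assumptions.

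| Assumed s | Deaths missing | Tabulated rate |
|---|---|---|
| 0% | 0 | 3.0% |
| 5% | 0.6 | (11.88 − 0.59)/396 = 2.9% |
| 10% | 1.2 | (11.88 − 1.19)/396 = 2.7% |
| 25% | 3.0 | (11.88 − 2.97)/396 = 2.3% (2.25% before rounding) |

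One death missing from one arm would lower that arm from 5.94/198 = 3.0% to 4.94/198 = 2.5%.

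**The case against.** A reader might infer that the protocol and the SAP contradict each other and that every post-dose worsening of an earlier condition drops out of every TEAE table. The documents do not support that. Protocol 10.2.1 says what an AE is; SAP 11.6.1 says when an AE is treatment-emergent. Under the protocol wording the exacerbation is itself the AE, with the underlying condition held in medical history, so one entered with its own onset meets the SAP rule.

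Other points on that side also carry weight:

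- Protocol 10.2.3 treats an SAE as resolved once the infant is back to Day 1 status. A relapse after that is naturally a new event. This does not help when the event was never closed.
- Infants must have completed acute stabilization before enrollment, and 7 days is the maximum window. This limits how many events are open at first dose.
- The rule also over-includes: Day 1 events before dosing and events with unknown timing count as TEAEs. So the rule as a whole does not only lower counts; the one-way effect is confined to routes (c) and (d).
- Re-hospitalizations for acute non-surgical illness through Day 56 are compared by arm in the Safety population with no TEAE filter (SAP 11.5.7). Deterioration that leads to readmission is visible there. Later events, and deaths without readmission, are not.
- The IDMC sees unblinded safety data. That protects participants during the trial but does not repair the final tables.
- The eCRF completion guidelines mentioned in SAP 11.4 may state an onset convention. They are not among the documents, so it cannot be said that every worsening SAE keeps its earlier date.

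These points narrow the concern. None of them reclassifies an event that does carry a pre-dose start date and worsens under that record.

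**Conclusion.** The point holds for two groups: AEs or SAEs that open between consent and first dose and then worsen, become serious or prove fatal under the same record, and conditions detected after dosing but recorded with a pre-dose onset. Both are left out of the TEAE-restricted by-arm summaries, including the death row, although they remain in the listings. It does not hold for exacerbations entered with their own post-dose onset.

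The number affected cannot be derived. The illustrative 0 to 3 deaths rest entirely on the assumed shares, and the 3% is a planning figure whose follow-up period is not stated. The case for the change does not depend on those shares: with about 6 deaths expected per arm, a death row that can miss even one is a weak basis for comparing the arms.

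**What to change.** Make three changes before unblinding:

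1. **Definition (SAP 11.6.1).** Define a TEAE as an AE that starts on or after the date of first dose, or that starts earlier and increases in severity or becomes serious or fatal on or after that date.
2. **One recording convention.** Choose either a new record with its own onset date, or the original record flagged as worsened with the date of worsening. Do not use both: the tables also report the number of AEs, so one worsening could be counted twice. If a new record is used, the original must not also become a TEAE because of the same worsening. State in the same place which onset date applies to a condition first found after dosing.
3. **Deaths.** Add a by-arm count of all deaths on or after first dose in the Safety population, by date of death, whatever the onset date of the linked AE. The death listing already holds the date.

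The cost is a SAP wording change, one added table row and a line in the eCRF completion guidelines. Some records may need a query for the date of worsening. Some deterioration of the admission illness unrelated to the product will be counted as treatment-emergent in both arms, which is a small price in a blinded comparison.

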the control group [Frese 2017]. The dominance of *B. infantis* influenced beta diversity (diversity between samples). However, there were no differences in terms of microbial species richness (alpha diversity) as the Shannon diversity index was similar between control and *B. infantis* groups. Lack of differences in alpha diversity between control and *B. infantis* is consistent with previous reports on breast-fed infants. Brink, et al, reported lower alpha diversity in infants receiving human milk compared to infant formula [Brink 2020].

Of note, the quality control of the study intervention will be important since contamination is a potential known risk for this type of product.

Bacterial transmigration and bacteremia have been described in case reports of *B. infantis* products but are considered coincidental, and not pathogenic. No bacterial transmigration or bacteremia cases have been reported with Bi-26 in ongoing infant clinical trials.

Potential benefits of supplementing infant feeding in low-income countries with *B. infantis* include a possible reduction in gut inflammation, and improved nutrient adsorption, potentially resulting in improved health outcomes. The findings from the SYNERGIE study with *B. infantis* strain EVC001 support the potential for positive clinical outcomes with *B. infantis* supplementation [Barratt 2022]. In the SYNERGIE study, following hospital discharge and acute phase management, infants were transferred to nutritional rehabilitation units and randomized to receive either 8 billion CFUs (target) of *B. infantis* EVC001 (n=20), 8 billion CFUs (target) or EVC001 plus probiotic LNnT (n=21), or lactose placebo (n=21). Infants received 4 weeks of supplementation and were followed for an additional 4 weeks for outcomes. Researchers observed that daily supplementation with *B. infantis* for 4 weeks was associated with *B. infantis* colonization and an increase in anthropometric measures, including WAZ [Barratt 2022]. This study provides support for a larger study assessing weight gain in underweight infants following supplementation with other *B. infantis* strains.

3. Objectives and Endpoints

See Table 1.

4. Study Design

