9.4. Primary Statistical Hypotheses and Sample Size Determination

The primary study hypothesis is that the difference in the mean change from baseline in WAZ is larger for participants randomized to at least 28 days of Bi-26 relative to placebo.

For the sample size calculation for the primary hypothesis, it is assumed that the between_group difference in the WAZ change from baseline is 0.45 with a standard deviation of 1.3. Based on the above assumption(s) using a 2-sided alpha of 5% and a power of at least 90%, a total of 354 participants, 177 in each group, is required.

Assuming a 10% loss to follow-up and a 3% mortality rate, a sufficient number of participants will be screened to ensure approximately 396 randomly assigned participants are enrolled, 198 in each treatment group.

Figure 2: Sample size sensitivity

N/group, 1-sided α =2.5%, Power=90%

9.5. **Populations for Analyses**

For purposes of analysis, the following populations are defined:

- Intention-to-treat (ITT) population: All participants randomly assigned to study intervention.
- **Modified intention-to-treat (mITT) population**: All participants randomly assigned to study intervention, who received at least one dose (including a partial dose) of the study intervention. Participants will be analyzed according to the intervention they were randomized.
- **Per-Protocol (PP) population**: All participants randomly assigned to study intervention, who received the study intervention, have a Day 90 visit, and did not substantially deviate from the protocol procedures. Participants will be analyzed according to the intervention they actually received. Details of criteria for defining the PP population will be specified in the Statistical Analysis Plan (SAP). The inclusion of participants in the PP population will be determined prior to unblinding the study. A participant data listing and a table with protocol deviations will be presented.
- **Safety population**: All participants randomly assigned to study intervention, who received any dose, including a partial dose, of the study intervention. Participants will be analyzed according to the intervention they actually received.

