6.2.1 Secondary Objectives

The safety of Bi-26 supplementation will be evaluated through EoS in the Safety population which includes, but is not limited to, the frequency (and percentages) of AEs, and all SAEs through the Day 90 visit. Individual results and descriptive statistics will be provided by treatment group.

Individual results and descriptive statistics for presence of *B. infantis* in stool will be provided at each time point by treatment group.

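### Adverse events, serious events and deaths are reported per arm only, with no between-arm interval to Day 90 and no pre-specified grouped term for invasive infection

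*SAP*

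**What the plan says.** Protocol 4.1 and SAP 7.1 give the study two aims: to show greater weight gain and to evaluate safety. Protocol Table 1 makes safety an other-secondary objective, measured by counts of adverse events (AEs) and serious adverse events (SAEs) to Day 90.

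The analysis is descriptive. SAP 6.2.1 states: "Individual results and descriptive statistics will be provided by treatment group". SAP 11.6.1 has these layers:

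- An overview table, introduced as "An AE overview table containing the number and percentage (expressed in percent) of participants with AEs from Day 1 through Day 90". Its rows combine all terms and include serious treatment-emergent AEs (TEAEs) and serious TEAEs that ended in death.
- Tables by system organ class (SOC) and preferred term, also n and % per arm.
- By-period and subgroup summaries, and listings.

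SAP 11.6.2 adds a death listing with primary cause. SAP 11.6.3 notes that no laboratory safety data are collected.

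Protocol 2.2 makes two separate statements about hazards of a live product. On quality control: "contamination is a potential known risk for this type of product". On case reports: "Bacterial transmigration and bacteremia have been described in case reports of" *B. infantis* products. The protocol regards these reported cases as coincidental rather than disease-causing, and says none have been reported with Bi-26 in ongoing infant trials.

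SAP 11.5.7 gives re-hospitalisation for acute non-surgical illness an adjusted rate ratio and an adjusted risk ratio (or odds ratio), each with a 95% interval, in the Safety population through Day 56.

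**The concern.** With about 200 infants per arm, the trial can make only a bounded statement about harm. Two bare percentages do not show that bound, and similar percentages are easily read as evidence of no difference. The SAP gives re-hospitalisation a between-arm estimate with an interval but gives none to death or serious TEAEs.

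The second issue is how infection events are counted. Sepsis, bacteraemia, septic shock and similar diagnoses are different preferred terms, so an excess could appear as several rows of one to three events. The SOC row does combine them, but with every other infection, and common minor infections would dilute an invasive subset. With no laboratory safety data, AE reports are the main source for such a signal. A list of terms chosen after unblinding would be open to the charge that it was chosen to fit the result.

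**Working it through.** **Inputs**

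- Arm size, Protocol 9.4: "approximately 396 randomly assigned participants are enrolled, 198 in each treatment group". The Safety population can only be this size or smaller.
- Mortality, Protocol 9.4: "Assuming a 10% loss to follow-up and a 3% mortality rate".
- No expected AE or SAE rate is given in either document. Every other event rate below is an assumption.

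**1. The plan's own sample size.** Protocol 9.4: "it is assumed that the between_group difference in the WAZ change from baseline is 0.45 with a standard deviation of 1.3", and "using a 2-sided alpha of 5% and a power of at least 90%, a total of 354 participants, 177 in each group, is required".

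- n per group = 2(1.960 + 1.282)² × 1.3² / 0.45² = 175.4, so 176 by the normal approximation. The noncentral t gives 177 (power 0.901). The stated 177 reproduces.
- Inflation: 354/0.90 = 393.3 (394); 354/(0.90 × 0.97) = 405.5 (406); 354/0.87 = 406.9 (407). The stated 396 is within 3% of all three.
- This calculation concerns weight-for-age only. The documents give no figure for safety precision.

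**2. Precision for death at 3%.** Expected deaths per arm: 0.03 × 198 = 5.9, about 6.

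- Wald half-width = 1.96 × √(2 × 0.03 × 0.97 / 198) = 0.0336, or 3.4 points.
- Newcombe, 6/198 in each arm: Wilson limits 1.40% to 6.45% around 3.03%. Half-width = √((3.03 − 1.40)² + (6.45 − 3.03)²) = 3.8 points.
- A doubling from 3% is an excess of 3.0 points, which lies inside both intervals.
- Power to detect that doubling at 198 per arm is 0.30.
- Even 0 versus 0 leaves ±1.9 points (Newcombe).

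**3. Effect of splitting by preferred term (assumed counts).** Take 12 versus 4 infants with an invasive infection, one event each, spread evenly over four preferred terms.

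| Display | Counts | Difference (points) | 95% interval | Fisher p |
|---|---|---|---|---|
| Each row | 3 v 1 | 1.0 | −1.5 to 3.9 (Newcombe) | 0.62 |
| Grouped | 12 v 4 | 4.0 | 0.2 to 7.9 (Wald); 0.05 to 8.4 (Newcombe) | 0.07 |

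Wald, grouped: 0.0606 − 0.0202 = 0.0404; SE = √(0.0606 × 0.9394/198 + 0.0202 × 0.9798/198) = 0.0197. The grouped result is borderline, not proof of harm.

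**4. The same question as a probability (assumed true rates).** Chance that a Newcombe 95% interval lies wholly above zero:

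| Grouped rates | Grouped term | One given term of four | At least one of four |
|---|---|---|---|
| 6% v 1% | 0.80 | 0.12 | about 0.40 |
| 4% v 1% | 0.46 | 0.03 | about 0.12 |

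The last column is 1 − (1 − p)⁴, treating the four terms as roughly independent. With Fisher p ≤ 0.05 instead, the grouped and single-term figures are 0.73 and 0.05 in the first row, and 0.35 and 0.01 in the second.

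**The case against.** The case for leaving the plan alone has several parts.

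- **The plan delivers the endpoint as worded.** It is a count of AEs and SAEs with descriptive statistics. There is no safety hypothesis, margin or rule for declaring safety. This stands: nothing here contradicts the protocol. A reader might infer that the trial is set to claim no difference in harm, but neither document says so. That is a risk in later reporting.
- **Events are already combined.** A reader might infer from the SOC and preferred-term tables that safety is shown only in fragments. It is not: the overview table combines serious TEAEs and deaths across all terms, SOC rows count each infant once, and the listings give term, cause and relatedness. This stands, but none of these displays compares the arms or isolates invasive infection.
- **A between-arm interval already covers much of the SAE burden.** Hospitalisation is an SAE criterion (Protocol 10.2.2), and re-hospitalisation has ratios with 95% intervals. This stands in part. That analysis stops at Day 56 while safety runs to Day 90, and a death outside hospital would not enter it.
- **The protocol does not treat bacteraemia as an established hazard.** A reader might merge contamination and bacteraemia into one acknowledged risk of Bi-26. Protocol 2.2 does not support that: it makes two statements, and discounts the bacteraemia reports. The case for a grouped term is that the protocol raised these topics and the trial population is more fragile than the healthy term infants of the product's intended use (Protocol 2.1).
- **The data monitoring committee sees unblinded safety data** (Protocol 8.4.5, SAP 7.1.2). This lowers the chance of missing an excess during the trial but does not shape the final report. The charter is not among the documents, so it cannot be said that the committee lacks such a grouping.
- **Any reader can compute an interval from the counts.** True for deaths and serious TEAEs. It is not true for a grouped infection term, because preferred-term rows cannot be summed without knowing which infants appear in more than one.

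**Conclusion.** The point holds as a gap in precision and reporting, and is worth fixing because the fix is cheap. SAP 11.6.1 and 11.6.2 plan no between-arm estimate or interval for AEs, serious TEAEs or deaths to Day 90, and no pre-specified grouped term for invasive infection.

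For death, the size rests on the plan's own figures: equal observed mortality of about 3% would leave a difference of 3.4 to 3.8 points open in either direction, enough to include a doubling. The gain from grouping rests wholly on assumed rates and an assumed even spread over four terms. It shows how a signal can be diluted, not that one is expected.

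**What to change.** In SAP 11.6.1, add one table of risk differences (Bi-26 minus placebo) through Day 90 in the Safety population, with 95% Newcombe or score intervals, which suit sparse counts better than Wald. Rows:

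1. Any serious TEAE.
2. Death.
3. One grouped term made up of sepsis, bacteraemia and other invasive bacterial infection preferred terms, each infant counted once.

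Fix the list of preferred terms before unblinding and attach it to the SAP. Label the intervals as descriptive. In the report, state the excess risk that each interval excludes, not only the two percentages. Offer the same grouping to the data monitoring committee if its charter does not already have one.

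Cost: agreeing a term list, programming one table, and a SAP amendment. No data collection or study procedure changes. The downside is a safety conclusion that looks less certain than bare percentages would suggest.
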